## **HYPOTHESES**

- a. VR distraction is a feasible and acceptable non-pharmacological method for procedural pain relief (during hydrotherapy) of young children with burn injuries.
- b. VR distraction combined with analgesics is more efficacious than standard treatment (analgesics alone) on procedural pain and anxiety (during hydrotherapy) of young children with burn injuries.

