## **METHODS**

**Design**. Single-arm pilot study.

**Sample and Setting**. Participants will be recruited through convenience sampling upon admission to the surgical-trauma burn unit. The unit has a hydrotherapy room for inpatients and outpatients. Healthcare professionals usually present during hydrotherapy are: a burn wound care nurse, a nurse clinician from the pain clinic, an anesthetist, a physical therapist and an orderly. The size of the total desired sample is 15 to 20 participants depending on the recruitment rate since it is a pilot study. The study will take place in the hydrotherapy room of the CHU St. Justine, a large pediatric university teaching hospital in Montreal where the VR prototype is installed.

Eligibility criteria. Inclusion criteria: children from 2 months to 10 years old, with a burn injury, requiring a hydrotherapy session for burn wound care, and accompanied by a consenting parent/legal tutor who can understand, read, and write either French or English. Exclusion criteria: 1) Admitted to the intensive care Unit, 2) Neuro-cognitive disability that precludes children from interacting with the distraction intervention, 3) Unconscious or intubated during hydrotherapy session, 4) Suffering from epilepsy (considering the nature of the intervention), 5) Allergic to opioids or other analgesics used for standard pharmacological treatment.

**Intervention**: The child will visualize and interact with the virtual environment throughout the hydrotherapy session. VR prototype developed by the SAT will be used as the experimental intervention. It has a wide screen installed at the end of the hydrotherapy tank offering a 150-degree field view, on which appears a game allowing the child to have the immersive entertainment experience without the need to wear a helmet or 3D glasses. The child or a proxy, depending on age and burn site, will have the opportunity to interact with the game. The interactive component is not mandatory for the immersive and distractive experiences provided by the prototype. Video

games tailored to the child's age and injury, different from the commercially available ones, will be adapted to each age-group of children recruited with control over the speed of movement to avoid motion sickness.

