**Measures**. Measures of baseline pain and anxiety will be recorded at T1, 30 minutes before the procedure, in the patient's room. Measures for procedural pain, anxiety and sedation level will be taken at: T2, before the procedure, upon arrival in the hydrotherapy room, T3, during the procedure (10 min after the beginning of the hydrotherapy session), T4, immediately after the procedure before leaving the hydrotherapy room and T5, 30 minutes after the procedure in the patient's room. The patient's comfort level will also be assessed during the procedure at T3. Finally, the acceptability of the intervention will be assessed through a questionnaire comprising items on the acceptability and satisfaction of the healthcare professionals at T4. The same measures will be recorded for each participant for up to three hydrotherapy sessions. The primary outcome will be the acceptability of the intervention. Comparisons will be made between pain and anxiety levels for the same order of session.

**A) Primary Outcome Measure**: Acceptability [Time Frame: T4, immediately after the procedure before leaving the hydrotherapy room]: To assess the acceptability including the satisfaction of healthcare professionals regarding the use of the VR prototype during the hydrotherapy session. Pre-tested tailored questionnaire including satisfaction and acceptability outcomes (tolerance, positive and negative aspects, secondary effects).

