### POSSIBLE PITFALLS AND SOLUTIONS

It is unknown whether the VR is a feasible distraction technique in young children/infants aged between 2 months and 2 years old. The pilot study will help inform the investigators about the visual tracking in infants during painful medical procedures. Upon completion of the pilot study, it will be decided whether to include or not the young population in the larger trial.

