## DATA ANALYSIS PLAN

Descriptive statistics will be performed for sociodemographic and clinical variables, comfort levels and the satisfaction of health professionals. Non-parametric inferential statistics will be used to compare the mean differences in pain scores before, during and after the procedure as well as for anxiety and level of sedation. Since the use of rescue medication is a potential indication of a treatment failure, the analysis will be supplemented by an analysis comparing the proportion of patients receiving rescue medication anytime during the procedure. Interpretation of the analyses will be made with reference to the data regarding rescue medication use. Data collected on dichotomous variables will be analyzed using a chi-square test and post-hoc analyses if the results are statistically significant.

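### Does the primary acceptability outcome need a stated rule for children who have more than one session?

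*Combined protocol and SAP*

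**What the plan says.** METHODS, Measures, lists pain, anxiety, sedation and comfort, then the questionnaire on acceptability and staff satisfaction at T4. It continues: "The same measures will be recorded for each participant for up to three hydrotherapy sessions". No measure is excepted, so the questionnaire is repeated too. The next two sentences are "The primary outcome will be the acceptability of the intervention" and "Comparisons will be made between pain and anxiety levels for the same order of session". The primary outcome entry gives T4 as the time frame, without a session number, and describes the target as staff satisfaction with using the prototype in the hydrotherapy session.

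The DATA ANALYSIS PLAN says: "Descriptive statistics will be performed for sociodemographic and clinical variables, comfort levels and the satisfaction of health professionals". It names no unit for that summary. It ends with a general provision for a chi-square test on dichotomous variables and does not say whether questionnaire items are included.

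On numbers, METHODS, Sample and Setting, says: "The size of the total desired sample is 15 to 20 participants depending on the recruitment rate since it is a pilot study". The staff usually present are "a burn wound care nurse, a nurse clinician from the pain clinic, an anesthetist, a physical therapist and an orderly". The documents do not say which of them complete the form.

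**The concern.** The authors saw that repeat sessions need handling and dealt with them for two secondary outcomes, but not for the primary one. The number of sessions can differ between children, and it may go with burn severity or growing familiarity, either of which could affect how staff rate the prototype. A summary over all sessions would then lean towards children with more sessions. Two analysts could both follow the plan and report different figures and denominators, one per child and one per session.

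The outcome bears on hypothesis (a), that "VR distraction is a feasible and acceptable non-pharmacological method for procedural pain relief (during hydrotherapy) of young children with burn injuries". A second worry is that repeated forms on the same child, often from the same staff, are not independent, so a count of forms would overstate the amount of information.

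**Working it through.** The plan states no power, error rate, effect size or expected acceptability, so there is no figure of its own to reproduce. The check is how far a pooled summary can differ from one in which each child counts once.

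**Inputs from the documents**
- 15 to 20 children (METHODS, Sample and Setting).
- 1 to 3 sessions per child (METHODS, Measures).

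One form per session would give 15 to 45 records for 15 children, or 20 to 60 for 20.

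**Assumed, because the documents do not say**
- How many children have three sessions and how many have one.
- The gap in acceptability between those two groups, on a percentage scale.
- The same number of replies at every session.

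**Weights.** If k of N children have three sessions and the rest have one, the k children supply 3k/(3k + N − k) of the sessions, against k/N of the children.

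| N | k | Share of sessions | Share of children | Excess weight |
|---|---|---|---|---|
| 15 | 5 | 15/25 = 60% | 33.3% | 26.7 points |
| 20 | 5 | 15/30 = 50% | 25% | 25 points |
| 20 | 7 | 21/34 = 61.8% | 35% | 26.8 points |
| 20 | 10 | 30/40 = 75% | 50% | 25 points |

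**Shift in the result.** With f = k/N and r = 3,

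pooled − per child = gap × f(1 − f)(r − 1)/(1 + (r − 1)f).

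At f = 0.35 this is gap × (0.35 × 0.65 × 2)/1.70 = gap × 0.268. The maximum over all f is gap × (√3 − 1)/(√3 + 1) = gap × 0.268, so 7 of 20 is about the worst split.

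- Assumed gap 0: no shift.
- Assumed gap 10, 20 or 40 points: at most 2.7, 5.4 or 10.7 points.
- Example: N = 15, k = 5, acceptability 90% in the three-session children and 60% in the others. Pooled: (15 × 90 + 10 × 60)/25 = 78%. Per child: (5 × 90 + 10 × 60)/15 = 70%. With the rates reversed: 72% against 80%.

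For scale, one child in 20 is 5 points. If all children have the same number of sessions, the weights are equal and the shift is zero.

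**If forms are counted instead of sessions.** Suppose all five usual roles reply at some sessions and only one at others. A child could then supply 1 to 3 × 5 = 15 forms. At r = 15 the limit is (√15 − 1)/(√15 + 1) = 0.59 of the gap. This rests on an assumption about respondents that the documents neither make nor exclude.

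**Independence.** With three records per child, the design effect is 1 + 2 × ICC. At an assumed ICC of 0.1, 0.5 or 0.9, 45 records are worth 45/1.2 = 37.5, 45/2.0 = 22.5 or 45/2.8 = 16.1 independent ones. This affects an interval or test, but not a plain description.

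**The texts side by side.** The primary outcome is rated by staff at the end of each session and refers to that session. A child treated three times gives three uses of the prototype. Counting three uses as three is correct if the question is how acceptable a session is; counting the child once is correct if the question is about the average child. The plan does not choose between them, but neither is wrong, and it nowhere says that forms will be put together without regard to session.

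**The case for a change.** The strongest case for a change is that a descriptive summary still needs a denominator and a weighting, that this is the primary outcome, and that a few sentences would settle both before any data are seen. The plan already has a principle, same order of session, that could be extended. The chi-square provision strengthens the case: tolerance or secondary-effect items could be yes/no, and an ordinary chi-square test on repeated forms would treat correlated replies as independent.

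Part of this stands. The unit and the respondents are not stated, and repeated forms should not be tested as though independent. But the plan lists satisfaction under descriptive statistics, and the chi-square sentence does not single out the questionnaire. Avoiding that error is ordinary practice.

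The rest is weaker. Making the first session primary would be a preference with a cost: if every one of 20 children had three sessions, 40 of 60 recorded sessions would drop out of the primary summary, and first-session ratings may reflect novelty or start-up problems. No acceptance threshold is attached to hypothesis (a), so no documented decision turns on a few points either way. The later choice about infants, "Upon completion of the pilot study, it will be decided whether to include or not the young population in the larger trial", follows a passage on feasibility and visual tracking in infants and is not tied to this form.

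**Conclusion.** No change to the plan follows. The documents leave the unit of the acceptability summary open, and analysts can fill that gap sensibly: tabulate by session order and give the numbers of children, sessions and forms, so that a reader can see any imbalance. No stated rule produces a wrong result, and a per-session summary fits the outcome as defined.

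The possible difference between pooled and per-child summaries is at most about 27% of the gap between three-session and one-session children, in either direction. It is zero when session counts are equal or acceptability does not vary with them. The limit assumes equal replies per session; with very unequal replies it could be larger. The session split and the gap are both assumptions, since the documents give neither. In a single-arm pilot of 15 to 20 children with a descriptive summary and no threshold, this is missing detail and a choice between two reasonable targets.

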# **B) Secondary Outcome Measures:**

- 1) Pain intensity [Time Frame: T1, 30 minutes before the procedure (patient's room); T2, upon arrival at the hydrotherapy room; T3, 10 min after the beginning of the hydrotherapy session; T4, immediately after the session before leaving hydrotherapy room; T5, 30 min. after the session]: Face, Legs, Activity, Cry and Consolability (FLACC).
- 2) Anxiety Level [Time Frame: T2, upon arrival at the hydrotherapy room; T3, 10 min after the beginning of the hydrotherapy session; T4, immediately after the session before leaving hydrotherapy room; T5, 30 min. after the session]: Procedure Behaviour Check List (PBCL).

- 3) Comfort Level [Time Frame: T3, during the procedure (10 min after the beginning of the hydrotherapy session)]: Behavioural observation scale of comfort level for child burn victims (OCCEB- BECCO).
- 4) Analgesic requirement [Time Frame: T3, during the procedure (10 min after the beginning of the hydrotherapy session)]: rescue dose medication administration.
- 5) Sedation level [Time Frame: T2, before the procedure, upon arrival in the hydrotherapy room, T3, during the procedure (10 min after the beginning of the hydrotherapy session), T4, immediately after the procedure before leaving the hydrotherapy room]: Ramsay sedation scale.
- 6) Baseline anxiety level [Time Frame: T1, 30 minutes before the procedure, in the patient's room]: Modified Smith Scale.

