### CONTRIBUTION AND EXPECTED RESULTS

Despite growing interest in the field, procedural pain management in children remains suboptimal and the importance of developing more effective methods is required. This project will provide

preliminary evidence on the feasibility, acceptability, and preliminary efficacy of non-pharmacological methods of procedural pain management through the development and testing of innovative interventions. VR distraction could be an interesting method to relieve pain, easy to use and without known side effects. The investigators hope that it could reduce the need for opioids and anxiolytics in burn children and decrease the pain related to the procedures while providing a less traumatizing hospital experience, which is often the first for children under 5 years old. The expected results have a direct effect on physical (pain, comfort) and psychological (anxiety) health of the child. In addition, clinical implications may include other indicators of quality of care and economic benefits such as duration of the hydrotherapy session, the amount of opioids and anxiety drugs administered, the use of coanalgesics, the number of professionals required in the hydrotherapy room and duration of wound healing.

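### Secondary effects are collected only by the T4 questionnaire; no nausea, vomiting or motion-sickness item is listed before exposure or at the planned T5 contact

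*Combined protocol and SAP*

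**What the plan says.** Under METHODS, A) Primary Outcome Measure, the time frame is stated outright: "Acceptability [Time Frame: T4, immediately after the procedure before leaving the hydrotherapy room". The instrument is a "Pre-tested tailored questionnaire including satisfaction and acceptability outcomes (tolerance, positive and negative aspects, secondary effects"). The Measures paragraph describes it as "a questionnaire comprising items on the acceptability and satisfaction of the healthcare professionals at T4". This is the only place in the document where secondary effects appear as something to be recorded.

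A later contact is already planned: "T5, 30 minutes after the procedure in the patient's room". The outcome list places pain there ("T5, 30 min. after the session]: Face, Legs, Activity, Cry and Consolability (FLACC")) and anxiety on the PBCL. The Measures paragraph adds sedation at T5, but the outcome list ends the Ramsay scale at T4. Neither lists a symptom item at T1, T2 or T5.

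The protocol recognises the symptoms in question. The Intervention paragraph says that games will be adapted "with control over the speed of movement to avoid motion sickness". BACKGROUND names nausea and vomiting among the side effects of opioids and anxiolytics. CONTRIBUTION AND EXPECTED RESULTS says that VR could be "easy to use and without known side effects". DATA ANALYSIS PLAN names no summary of secondary effects.

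**The concern.** Tolerance and secondary effects are components of the primary outcome, and the display is a new prototype. Under POSSIBLE PITFALLS AND SOLUTIONS, the pilot is to inform whether the youngest children enter the larger trial.

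If symptoms are sought only before the child leaves the hydrotherapy room, a report of few or none could partly reflect when they were looked for. With no record before exposure, a symptom seen at T4 also cannot be separated from one that the child already had on arrival.

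Because the plan fixes the questionnaire at T4, this is a consequence of following the plan as written, and not a detail left open.

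**Working it through.** **Step 1: the schedule, side by side.** Taken from METHODS (Measures; A) Primary Outcome Measure) and B) Secondary Outcome Measures.

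| Time | Listed measures | Nausea, vomiting or motion-sickness item |
|---|---|---|
| T1, 30 min before | Pain, baseline anxiety | None |
| T2, arrival | Pain, anxiety, sedation | None |
| T3, 10 min in | Pain, anxiety, comfort, sedation, rescue medication | None |
| T4, end of session | Pain, anxiety, sedation, acceptability questionnaire | Secondary effects, within the questionnaire |
| T5, 30 min after | Pain, anxiety; sedation in the Measures paragraph only | None |

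FLACC or PBCL at T5 might register distress caused by nausea, but would not identify it as nausea.

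**Step 2: what the gap could do.** The plan gives no side-effect rate, onset time or related calculation, so there is no figure to reproduce. The following is illustration under assumed inputs.

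- n = 15 or 20: from Sample and Setting.
- p = proportion of children with a symptom by T5: assumed 5%, 10% or 20%.
- f = share of those cases that begin after T4: assumed 25%, 50% or 75%.
- Each child is treated as observed once, and every case that has begun by a recording point is taken to be recorded.

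Chance of recording at least one case:

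- T4 only: 1 − [1 − p(1 − f)]^n
- T5 also covered: 1 − (1 − p)^n

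Worked example, n = 15, p = 0.10, f = 0.50: T4 only is 1 − 0.95^15 = 53.7%; with T5 it is 1 − 0.90^15 = 79.4%.

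| n | p | T5 covered | T4 only, f = 25% | f = 50% | f = 75% |
|---|---|---|---|---|---|
| 15 | 5% | 53.7% | 43.6% | 31.6% | 17.2% |
| 15 | 10% | 79.4% | 68.9% | 53.7% | 31.6% |
| 15 | 20% | 96.5% | 91.3% | 79.4% | 53.7% |
| 20 | 5% | 64.2% | 53.4% | 39.7% | 22.2% |
| 20 | 10% | 87.8% | 79.0% | 64.2% | 39.7% |
| 20 | 20% | 98.8% | 96.1% | 87.8% | 64.2% |

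**Step 3: what sample size alone implies.** With zero events, the exact two-sided 95% upper limit is 1 − 0.025^(1/n): 21.8% for n = 15 and 16.8% for n = 20. These limits would apply even with complete capture, so they are no evidence about timing. Under the present schedule they would cover only effects seen by T4.

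**The case against.** The strongest reply is that T4 covers the whole exposure. VR runs through the session, T4 is at its end, a pain-clinic nurse and an anesthetist are usually in the room, tolerance is already a named item, and the measures repeat for up to three sessions. What is left uncovered is onset or first notice in the next 30 minutes, and nothing in the documents indicates that this is common. This stands, and it is why no size can be claimed. Repeated sessions also give further chances to record a symptom, which the illustration ignores. But they do not close the gap, because each session ends its recording at the same point.

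A reader might infer that all side effects are recorded only at T4. The documents do not support that: sedation, which BACKGROUND links to the medication, is measured separately on the Ramsay scale.

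A reader might also infer that later events are certainly missed. The documents support only that no described study measure would capture them. Ward charting might note an episode, but it is not made study data. Nor is it stated outright who completes the questionnaire; staff is the natural reading.

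Two objections to the obvious remedy also hold. A baseline at T1 may precede analgesia, whose timing is not stated, so T2 is the better existing time point. And children as young as 2 months cannot report nausea or dizziness, so the items must be observer-based.

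Finally, the wording in CONTRIBUTION AND EXPECTED RESULTS is conditional and refers to known effects. It should not be read as a planned safety conclusion.

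**Conclusion.** The point holds for nausea, vomiting and motion-sickness symptoms within the study measures described. As written, a symptom that begins or is first noticed between T4 and T5 does not enter the tolerance part of the primary outcome, and one present before exposure is not identified as such.

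The size is unknown. In the illustration at an assumed 10% rate, the loss in the chance of recording any case runs from about 10 percentage points (79.4% − 68.9% = 10.5 for n = 15; 87.8% − 79.0% = 8.8 for n = 20) to nearly 50 (79.4% − 31.6% = 47.8; 87.8% − 39.7% = 48.1) as the late share goes from 25% to 75%. It rests entirely on the assumed rate and late share, and on one observation per child.

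The gap weakens one component of the primary outcome. It does not invalidate the pilot, and it is not evidence that VR causes symptoms. It should be corrected because the contacts needed already exist.

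**What to change.** - **Collection.** Add the same short yes/no items at T2, T4 and T5 of each of the up to three sessions: vomiting, apparent nausea, and unsteadiness where assessable. The parent or nurse reports them, with a one-line observable definition for each. At T4, add a line recording whether VR was stopped early because of symptoms. This records what happened and sets no rule for stopping.
- **Analysis.** In DATA ANALYSIS PLAN, define a new symptom as absent at T2 and present at T4 or T5. Report the number of children with one, per child and per session, with an exact 95% interval for the per-child proportion. State that it cannot be attributed to VR without a control group.
- **Consistency.** Reconcile the Measures paragraph and the outcome list on whether sedation is measured at T5.

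**Cost.** A few extra tick boxes per session at existing contacts, with no added visit. The downside is that some recorded symptoms will be due to opioids. The T2 baseline reduces this but cannot remove it, since medication may also be given during the session.
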